Official Study Title: The Efficacy of Adjuvant Oral Care in Prevention of Ventilator-Associated Pneumonia

- **ClinicalTrials.gov Identifier**
 - **NCT06039995**
- **Study Design**
 - Randomized Controlled Trial
- **Sponsor / Responsible Party**
 - University of Health Sciences
- **Study Site**
 - Services Hospital, Lahore, Pakistan
- **Principal Investigator**
 - [name]
 - University of Health Sciences
- **Document Type**
 - Study Protocol
- **Protocol Version**
 - Version 1.0
- **Document Date**
 - 15 December 2025

Study Protocol

▪ Title

- The Efficacy of Adjuvant Oral Care in the Prevention of Ventilator-Associated Pneumonia: A Randomized Controlled Trial

▪ Background and Rationale

- Ventilator-associated pneumonia (VAP) is a common and serious complication among mechanically ventilated patients in intensive care units (ICUs). Oral colonization by pathogenic microorganisms is a recognized contributor to VAP development. Enhanced oral care strategies combining mechanical and chemical interventions may reduce microbial load and subsequent pulmonary infection. This study evaluates whether adjuvant oral care provides benefit beyond traditional oral hygiene practices.

▪ Objectives

• Primary Objective:

- To compare the incidence of ventilator-associated pneumonia between patients receiving adjuvant oral care and those receiving traditional oral care.

• Secondary Objectives:

- To compare the duration of ICU stay between the two groups.
- To compare mortality rates during ICU admission between the two groups.

▪ Study Design

- This was a single-centre, parallel-group, randomized controlled trial conducted over a three-month period at Services Hospital, Lahore. A total of 100 mechanically ventilated adult patients were enrolled and randomly allocated in a 1:1 ratio to either the intervention or control group.

▪ Study Population

- Adult patients (18–65 years) admitted to the ICU and receiving mechanical ventilation were eligible. All participants were enrolled from Pakistan. Baseline characteristics, including age and sex distribution, were comparable between groups.

▪ Interventions

• Intervention Group (Adjuvant Oral Care):

Patients received comprehensive oral care consisting of:

- 0.2% chlorhexidine mouthwash
- Mechanical toothbrushing using chlorhexidine
- Application of moisturizing gel to interior and exterior oral surfaces

• Control Group (Traditional Oral Care):

- Patients received routine oral care using cotton swabs dipped in 0.2% chlorhexidine mouthwash only.

▪ Outcome Measures

• Primary Outcome: Incidence of ventilator-associated pneumonia during ICU stay.

• Secondary Outcomes: Duration of ICU stay (days) and mortality during ICU admission.

▪ Ethical Considerations:

The study was conducted following approval from the relevant human subject's protection review board. No protocol amendments affecting all study sites were reported. There were no restrictions on publication rights for investigators.

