Title: The Efficacy of Adjuvant Oral Care in Prevention of Ventilator-Associated Pneumonia

- **ClinicalTrials.gov Identifier**
 - **NCT06039995**
- **Study Design**
 - Randomized Controlled Trial
- **Sponsor / Responsible Party**
 - University of Health Sciences
- **Study Site**
 - Services Hospital, Lahore, Pakistan
- **Principal Investigator**
 - [name]
University of Health Sciences
- **Document Type**
 - Statistical Analysis Plan (SAP)
- **SAP Version**
 - Version 1.0
- **Document Date**
 - 15 December 2025

Statistical Analysis Plan (SAP)

• Analysis Population

- All randomized participants (n=100) were included in the analysis, with 50 patients in each study arm. No attrition was reported.

• Descriptive Statistics

- Continuous variables (age, ICU stay) were summarized using means and standard deviations.
- Categorical variables (sex, VAP incidence, mortality) were summarized using frequencies and percentages.

• Primary Outcome Analysis

- The incidence of VAP was compared between intervention and control groups using a chi-square test or Fisher's exact test, as appropriate. The level of statistical significance was set at $p < 0.05$.

• Secondary Outcome Analyses

- **Duration of ICU Stay:** Compared between groups using an independent-samples t -test, assuming approximate normality.
- **Mortality Rates:** Compared using chi-square analysis.

• Assumptions and Verification

- Normality assumptions for continuous outcomes were assessed using descriptive distribution checks.
- Equality of variances was evaluated prior to parametric testing.
- No adjustments for multiple comparisons were applied, as secondary outcomes were exploratory.

• Handling of Missing Data

- No missing outcome data were reported; therefore, no imputation methods were required.

• Safety Analysis

- Adverse events were summarized descriptively. Serious and non-serious adverse events were compared between groups. No intervention-related adverse events were reported.

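### The ICU-stay outcome has no stated start; if it runs from ICU admission, days before randomisation enter the t-test and may cost precision

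*Protocol*

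**What the plan says.** The protocol's Objectives include a secondary one: "To compare the duration of ICU stay between the two groups". Under Outcome Measures the corresponding entry is "Duration of ICU stay (days) and mortality during ICU admission". The unit is days, but neither document gives the event that starts the count or the one that ends it.

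On entry to the trial, Study Population says: "Adult patients (18–65 years) admitted to the ICU and receiving mechanical ventilation were eligible". No section sets a maximum time from ICU admission, or from the start of ventilation, to randomisation.

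The SAP, under Secondary Outcome Analyses, says of ICU stay: "Compared between groups using an independent-samples t -test, assuming approximate normality". No covariate is named. Under Assumptions and Verification it describes the secondary outcomes as exploratory and applies no multiplicity adjustment. The baseline characteristics that the documents name are age and sex; time already spent in the ICU is not among them.

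**The concern.** Read in the usual way, a patient's ICU stay is the sum of two parts: days from ICU admission to randomisation, and days from randomisation onward. Trial oral care can act only on the second part. The first was fixed before allocation, so it carries no treatment effect, yet with an unadjusted t-test on the sum its variation goes into the standard error.

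If patients were enrolled at widely different points in their ICU stay, the comparison would be less able to show a difference than the same 100 patients would allow. A reader could not tell whether this happened, because the plan neither defines the start of the count nor asks for the delay to be described.

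**Working it through.** **Is there a figure to reproduce?** No. The documents give no SD, target difference, power or sample-size derivation for ICU stay. The one check available is the allocation: 100 patients at 1:1 is 100/2 = 50 per arm, which agrees with the SAP's Analysis Population.

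**Inputs**
- From the documents: 50 patients per arm, all analysed; unadjusted two-sample t-test; significance level 0.05 (stated under the primary outcome, taken here as two-sided and applied to ICU stay).
- Assumed, because the documents give nothing: SD of post-randomisation stay, s1 = 6 days; SD of the admission-to-randomisation delay, s0 = 1 to 4 days; their correlation r = 0, then −0.2 and +0.3.

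**Step 1: variance of total stay.** Var(total) = s1² + s0² + 2·r·s0·s1. With r = 0:
- SD inflation = √(s1² + s0²)/s1
- Effective sample = 100 × s1²/(s1² + s0²)
- SD of the chance difference in mean delay between arms = s0 × √(1/50 + 1/50) = 0.2 × s0

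| s0 (days) | Var(total) | SD inflation | Effective sample of 100 | SD of chance difference (days) |
|---|---|---|---|---|
| 0 | 36 | 1.000 | 100 | 0 |
| 1 | 37 | 1.014 | 97 | 0.2 |
| 2 | 40 | 1.054 | 90 | 0.4 |
| 3 | 45 | 1.118 | 80 | 0.6 |
| 4 | 52 | 1.202 | 69 | 0.8 |

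The last column is not a harm on top of the others. The t-test's standard error already contains that variation.

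**Step 2: let the correlation vary.** Effective sample = 100 × 36/Var(total), with the term 2·r·s0·6 added:

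| s0 | r = −0.2 | r = +0.3 |
|---|---|---|
| 1 | 36/34.6 → 104 | 36/40.6 → 89 |
| 2 | 36/35.2 → 102 | 36/47.2 → 76 |
| 3 | 36/37.8 → 95 | 36/55.8 → 65 |
| 4 | 36/42.4 → 85 | 36/66.4 → 54 |

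Total stay is no noisier than post-randomisation stay when r ≤ −s0/(2·s1). For s1 = 6 those limits are −0.08, −0.17, −0.25 and −0.33 at s0 = 1, 2, 3 and 4. A modest negative correlation therefore removes the loss from a small delay, but not from a large one.

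**Step 3: the same effect as power, with other assumed SDs.** With 50 per arm, 80% power needs a difference of (1.960 + 0.842) × √(2/50) = 0.56 SD. Hold that difference fixed, set r = 0, and use power = Φ(difference/(SD(total) × √(2/50)) − 1.960):

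| s1 | Difference (days) | s0 = 0 | s0 = 1 | s0 = 2 | s0 = 3 | s0 = 5 |
|---|---|---|---|---|---|---|
| 5 | 2.8 | 80% | 78% | 74% | 67% | 51% |
| 8 | 4.5 | 80% | 79% | 78% | 75% | 66% |

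What matters is the spread of the delay relative to the spread of later stay. A delay that is the same for everyone costs nothing.

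**The case against.** The strongest objection is that the premise is inferred. The documents never speak of whole or total stay and never say that the count begins at admission. A reader might infer that the authors chose to count days before randomisation. The text supports only that the start is undefined, with admission as its ordinary meaning. That stands, and the point is conditional for this reason.

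Second, no delay is documented. The eligibility wording, "admitted to the ICU and receiving mechanical ventilation were eligible", fits randomisation on the day of admission just as well as a week later. That also stands: the loss could be nil, and every SD and correlation used above is assumed.

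Third, a reader might infer that the ICU-stay comparison is biased, or that chance imbalance in late-enrolled patients could produce false positives. The documents do not support either. Randomisation balances earlier days in expectation, and the t-test's standard error already allows for their variation.

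Fourth, the consequence is limited. The SAP calls this outcome exploratory, and nothing here touches the primary VAP comparison.

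Finally, both documents are written in the past tense about a completed trial. Changing the start of the count now redefines an outcome that has already been compared. This does not cancel the point, but it governs how the fix must be presented.

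**Conclusion.** The point holds as a minor, conditional one. The start of the ICU-stay count is not stated. On the ordinary reading, the outcome includes days that neither regimen could influence, no enrolment window limits them, and the planned test does not adjust for them. Counting from randomisation would be a better-targeted measure.

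The size cannot be settled from the documents. Under the assumed SD of 6 days and an independent delay, the effective sample lies between 97 and 69 of 100 for delay SDs of 1 to 4 days. Allowing the correlation to range from −0.2 to +0.3 widens this from no loss at all to about 54. If patients were enrolled within about a day of admission the issue is negligible; if the delay varied by several days it is material for this outcome. In either case what is at stake is precision, not the validity of the test.

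**What to change.** 1. State when the ICU-stay count starts and stops.
2. If randomisation dates were recorded, compare ICU days from randomisation to ICU discharge or death. Alternatively, keep total stay and adjust for ICU days before randomisation in a linear model. Total stay minus the earlier days is the later stay, so the adjusted comparison has residual variance s1² × (1 − r²) whichever of the two is the outcome. Apart from one degree of freedom, it is never less precise than the unadjusted comparison of either.
3. Report the delay from ICU admission to randomisation by arm with the baseline characteristics. This alone would show whether the matter is trivial.
4. Keep total ICU stay as a reported figure, and label the recalculated comparison as a post hoc clarification or sensitivity analysis.

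The cost is a line in each document, one baseline row and a recalculation. It depends on randomisation dates being available, which the documents do not confirm. There are two drawbacks. It is a post hoc redefinition of an outcome already compared, so both versions should be shown. And a count that ends at death still scores an early death as a short stay, so the result should be read beside ICU mortality.

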Title: The Efficacy of Adjuvant Oral Care in Prevention of Ventilator-Associated Pneumonia

- **ClinicalTrials.gov Identifier**
 - **NCT06039995**
- **Study Design**
 - Randomized Controlled Trial
- **Sponsor / Responsible Party**
 - University of Health Sciences
- **Study Site**
 - Services Hospital, Lahore, Pakistan
- **Principal Investigator**
 - [name]
University of Health Sciences
- **Document Type**
 - Statistical Analysis Plan (SAP)
- **SAP Version**
 - Version 1.0
- **Document Date**
 - 15 December 2025

Statistical Analysis Plan (SAP)

• Analysis Population

- All randomized participants (n=100) were included in the analysis, with 50 patients in each study arm. No attrition was reported.

• Descriptive Statistics

- Continuous variables (age, ICU stay) were summarized using means and standard deviations.
- Categorical variables (sex, VAP incidence, mortality) were summarized using frequencies and percentages.

• Primary Outcome Analysis

- The incidence of VAP was compared between intervention and control groups using a chi-square test or Fisher's exact test, as appropriate. The level of statistical significance was set at $p < 0.05$.

• Secondary Outcome Analyses

- **Duration of ICU Stay:** Compared between groups using an independent-samples t -test, assuming approximate normality.
- **Mortality Rates:** Compared using chi-square analysis.

• Assumptions and Verification

- Normality assumptions for continuous outcomes were assessed using descriptive distribution checks.
- Equality of variances was evaluated prior to parametric testing.
- No adjustments for multiple comparisons were applied, as secondary outcomes were exploratory.

• Handling of Missing Data

- No missing outcome data were reported; therefore, no imputation methods were required.

• Safety Analysis

- Adverse events were summarized descriptively. Serious and non-serious adverse events were compared between groups. No intervention-related adverse events were reported.

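### Does leaving the choice between chi-square and Fisher's exact test open, with no continuity-correction rule, make the primary VAP analysis unsound?

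*SAP*

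**What the plan says.** Under Primary Outcome Analysis, the SAP states: "The incidence of VAP was compared between intervention and control groups using a chi-square test or" Fisher's exact test, whichever suits, with significance at p < 0.05. It does not state the criterion for choosing, the sidedness, or whether the chi-square carries a continuity correction.

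Under Secondary Outcome Analyses, mortality is "Compared using chi-square analysis", with no small-count alternative. Under Assumptions and Verification, the SAP calls the secondary outcomes exploratory.

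On the data, Analysis Population says: "All randomized participants (n=100) were included in the analysis, with 50 patients in each study arm. No attrition was reported". Handling of Missing Data adds: "No missing outcome data were reported; therefore, no imputation methods were required". The analysis of each binary outcome is therefore a single 2×2 table with 50 patients in each row.

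**The concern.** The usual convention (Fisher if any expected count is below 5, otherwise chi-square) settles which family of test applies, but not which chi-square. Uncorrected Pearson and the continuity-corrected version can give different verdicts on the same table. Software defaults differ too: for 10/50 vs 19/50, scipy's default gives p = 0.078 and statsmodels' default gives p = 0.047. Two competent analysts could then report opposite conclusions on the single primary endpoint.

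Two features sharpen the worry. The SAP is in the past tense and already reports complete data, so it appears to have been written after data collection, and an open choice of test is harder to defend at that stage. Mortality also has no Fisher option, so one low-count table could be significant as a mortality result and non-significant as a VAP result.

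**Working it through.** **Inputs.** 50 per arm and no missing outcomes (SAP, Analysis Population and Handling of Missing Data); threshold 0.05 (SAP, Primary Outcome Analysis). Two-sided testing is assumed, because a 2×2 chi-square is non-directional. The documents give no VAP rate, target effect or power, so every rate pair below is an assumption and there is no plan figure to reproduce.

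**Formulas.** Let a and b be the events in the two arms and m = a + b. The cross-product difference is D = |a(50 − b) − b(50 − a)| = 50|a − b|.

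- Pearson: X² = 100·D² / [50·50·m·(100 − m)]
- Continuity-corrected: replace D by D − 50
- Smallest expected count: min(m, 100 − m)/2

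**One table.** For 10/50 vs 19/50, m = 29, D = 450 and the smallest expected count is 14.5, so chi-square applies.

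- Denominator: 2,500 × 29 × 71 = 5,147,500
- Pearson: 100 × 450² / 5,147,500 = 3.934, p = 0.047
- Corrected: 100 × 400² / 5,147,500 = 3.108, p = 0.078
- Fisher: p = 0.077

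**All tables.** There are 51 × 51 = 2,601 possible tables. Pearson is significant in 1,834; the corrected test and Fisher are each significant in 1,740 and agree in every table. Pearson alone is significant in 1,834 − 1,740 = 94; the reverse never happens. Of the 94, 82 have all expected counts of at least 5 (41 per direction, arms differing by 6 to 10 events). In those 82, Pearson p runs from 0.025 to 0.050 and corrected p from 0.054 to 0.096.

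**Chance of a split.** Fisher is used when an expected count is below 5, otherwise the named chi-square. Tables are weighted by binomial probabilities at the assumed rates. The last column is the difference between the two power columns.

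| Assumed rates | Power, Pearson | Power, corrected | Opposite verdicts |
|---|---|---|---|
| 50% vs 10% | 99.7% | 99.4% | 0.3% |
| 40% vs 10% | 95.4% | 92.7% | 2.7% |
| 50% vs 20% | 89.5% | 85.3% | 4.2% |
| 60% vs 30% | 87.6% | 82.9% | 4.7% |
| 40% vs 15% | 81.9% | 75.8% | 6.1% |
| 50% vs 25% | 74.5% | 67.5% | 7.0% |
| 40% vs 20% | 59.5% | 51.5% | 8.0% |
| 30% vs 10% | 73.4% | 64.0% | 9.4% |
| 25% vs 10% | 52.9% | 41.0% | 11.9% |
| 20% vs 5% | 64.3% | 50.8% | 13.5% |

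With equal rates of 10% to 50%, the split probability is 1.9% to 2.4%. On a grid of 120 unequal pairs from 5% to 80% in 5-point steps, 79 pairs fall below the 6–9% band, 36 round into it and 5 lie above it.

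**Type I error.** The maximum over common rates is 5.69% with Pearson and 3.52% with the corrected version. Pearson is significant whenever either of the others is, so picking the most favourable of the three is the same as always using Pearson. Its maximum is also 5.69%.

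**Mortality.** For 0/50 vs 4/50, Pearson p = 0.041 and Fisher p = 0.117. With an expected count below 5, Pearson and Fisher disagree in only three low-count tables per direction: 0 vs 4, 0 vs 5 and 1 vs 7. Uncorrected Pearson has type I error of 1.3% at a common death rate of 2%, 4.3% at 5% and 5.1% at 10%.

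**The case for a change.** The strongest case for a change is reproducibility. This is the only primary endpoint of a 100-patient trial, and nothing in either document shows that the result will lie clear of the split band. Among the 43 grid pairs with power between 30% and 90%, the split probability is 4.2% to 13.5%, and 32 of them round to 6–9%. In the four mid-range scenarios (40 vs 15, 40 vs 20, 30 vs 10, 50 vs 25), 7% to 13% of the trials that Pearson would call positive lose that verdict under the corrected test. One sentence would remove the ambiguity.

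The arithmetic stands, and so does the observation that the SAP does not name the chi-square version. The inference that the primary test is therefore undetermined does not. It applies convention to the switching rule but withholds it from the word chi-square, which without qualification ordinarily means Pearson. The software example shows that defaults differ, but the documents name no package.

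The timing argument adds little. The past tense suggests the SAP followed data collection, but the documents do not show that the comparative VAP result was known when it was written, or that no earlier plan exists. A rule added now could not restore pre-specification, and the free-choice bound already limits the cost if sidedness is fixed at two-sided. The mortality example is a constructed table for an outcome the SAP treats as exploratory.

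**Conclusion.** No change to the plan is called for. The SAP omits a detail, but each sensible way of filling it gives a usable test at 50 per arm, with maximum two-sided type I error of 5.7% (Pearson) or 3.5% (corrected). The two differ by a familiar trade-off: in the four mid-range scenarios the corrected test gives up 6 to 9 points of power in return for conservatism. Naming either one would not bring in a better method than those the SAP lists.

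The size of the ambiguity depends on assumed VAP rates: 0 to 13.5% over the grid, and about 2% with no effect. It affects only tables near the threshold, where the evidence is borderline under either version. For mortality, uncorrected Pearson holds its error rate at or below about 5.1% at the common death rates examined (2% to 10%), so the missing Fisher option does not give a wrong analysis. These conclusions rest on two-sided testing, 50 analysed per arm and the usual expected-count rule.
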